9.1.1 Reporting of Adverse Events

Report initiation for all AEs and SAEs will begin at the time of the first treatment visit and continue up until the final study visit (i.e. up to NTF-FU2 for subject who do not experience virologic failure or until viral suppression is achieved for subjects who experience virologic failure). All events will be followed to resolution or until 30 days after the subject completes the study. A final assessment of outcome will be made at that time.

All AEs must be recorded in the subject's medical records and on the eCRFs. AEs will be reported using customary medical terminology along with the following information: the onset and end dates, whether the event is considered to be a SAE (see [Section 9.2](#)), the impact the event had on study treatment (see [Section 9.1.2](#)), the DAIDS AE grade (intensity) of the event (see [Section 9.1.3](#)), the causality of the event (see [Section 9.1.4](#)), whether treatment was given as a result of the event (see [Section 9.1.5](#)), and the outcome of the event (see [Section 9.1.6](#)).

9.1.2 Impact of Study Treatment

The impact the event had on the study treatment will be assessed as either: none, study treatment interrupted, study treatment discontinued, or not applicable. The "not applicable" assessment will be used only when the subject is no longer in the treatment phase of the protocol, or if the outcome of the event was "death".

9.1.3 DAIDS AE Grade (Severity) Assessment

The investigator will carefully evaluate the comments of each subject and the response to treatment in order to judge the true nature and severity of the AE. The question of the relationship of AEs to study drug should be determined by the investigator after thorough consideration of all available facts. To assess severity, the investigator will use the DAIDS AE grading table (for adverse events as well as any injection site reactions refer to [Section 16.2](#) and [Section 16.3](#)).

The general guidelines for assessing the AE grade appear below. Full guidelines may be obtained at http://rsc.tech-res.com/Document/safetyandpharmacovigilance/DAIDS_AE_Grading_Table_v2_NOV2014.

Table 9-1: DAIDS AE Grading Table v2 General Guidelines

Grade	Description
Grade 1	indicates a mild event
Grade 2	indicates a moderate event
Grade 3	indicates a severe event
Grade 4	indicates a potentially life-threatening event
Grade 5	Death related to AE.

DAIDS AE Grading Table Version 2.0- November 2014

9.1.4 Causality Assessment

Adverse events will be assigned a relationship (causality) to the study treatment. The Principal Investigator (PI) must review each AE and make the determination of relationship of the event to the study treatment. Relationship of AEs to study treatment will be classified as follows:

- Definitely related:** This category applies to those AEs that the Investigator feels are incontrovertibly related to the study treatment. An AE may be assigned an attribution of definitely related if or when it meets all of the following criteria: (1) it follows a reasonable temporal sequence from administration of the study treatment; (2) it could not be reasonably explained by the known characteristics of the subject's clinical state, environmental or toxic factors, or other modes of therapy administered to the subject; (3) it follows a known response pattern to treatment with the study treatment.
- Probably related:** This category applies to those AEs which, after careful medical consideration at the time they are evaluated, are felt with a high degree of certainty to be related to the study treatment. An AE may be considered probable if or when (must have three): (1) it follows a reasonable temporal sequence from administration of the study treatment. (2) It could not readily have been produced by subject's clinical state, environmental or toxic factors, or other therapies administered to the subject. (3) Disappears or is decreased upon discontinuation of the study treatment. (4) It follows a

known response pattern to treatment with the study treatment.

3. **Possibly related:** This category applies to those AEs which, after careful medical consideration at the time they are evaluated, are judged unlikely but cannot be ruled out with certainty to the study treatment. An AE may be considered possible if or when (must have two): (1) it follows a reasonable temporal sequence from administration of the study treatment. (2) It could not readily have been produced by subject's clinical state, environmental or toxic factors, or other therapies administered to the subject. (3) Disappears or is decreased upon discontinuation of the study treatment. (4) It follows a known response pattern to treatment with the study treatment.
4. **Remotely related:** In general this category can be considered applicable to those AEs which, after careful medical consideration at the time they are evaluated, are judged likely to be unrelated to the study treatment. An AE may be considered unlikely if or when (must have two): (1) it does not follow a reasonable temporal sequence from administration of the study treatment. (2) It could not readily have been produced by subject's clinical state, environmental or toxic factors, or other therapies administered to the subject. (3) Disappears or is decreased upon discontinuation of the study treatment. (4) It does not follow a known response pattern to treatment with the study treatment.
5. **Unrelated:** This category applies to those AEs which, after careful consideration at the time they are evaluated, are clearly and incontrovertibly due to extraneous causes (disease, environment, etc.) and determined with certainty to have no relationship to the study treatment.

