9.1.8 SC Injection-related Events

SC and IV injections of concentrated protein materials can be associated with injection-related AEs that impact the ability to safely and successfully deliver the drug. Local injection-site reactions may include pain/discomfort, induration, erythema, nodules/cysts, pruritus, ecchymosis, etc. For SC injections, bleeding, absorption of the drug, leakage of drug, and induration at the local injection site can be additional complications. Other AEs that are common to monoclonal antibody-based therapies are chills, headache, backache, malaise, fever, pruritus, rash, nausea, tingling, and hypertension.

SC injection-related events will be monitored according to the guidelines provided in [Section 16.2](#) (Division of AIDS Table for Grading the Severity of Adult and Pediatric Adverse Events [DAIDS AE Grading Table]). Injection-site reactions thought to be directly related to the injection are considered to be AEs of special interest, and a separate guideline for the acquisition of data related to this AE of special interest is provided in [Section 16.3](#).

For subjects who develop grade 1 or grade 2 events, continue therapy as per protocol. If a subject chooses to discontinue study treatment, the site should notify the protocol team leadership, and encourage the subject to complete any remaining study visits until the toxicity resolves.

For subjects who develop grade 3 events following study drug injection, the subject should be reevaluated closely until the AE returns to Grade ≤ 2 , at which time study treatment may be reintroduced at the discretion of the site investigator. If the *same* Grade 3 AE recurs following the next administration of study drug, study treatment must be permanently discontinued. Subjects experiencing Grade 3 AEs requiring permanent discontinuation of study treatment should be followed closely for resolution of the AE to Grade ≤ 2 and the team leadership must be notified.

Subjects with Grade 3 asymptomatic laboratory abnormalities in cholesterol, creatine kinase (CK) or triglycerides may continue study treatment.

For grade 4 events permanently discontinue therapy.

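### Two of the four criteria for *Remotely related* were left un-negated, so evidence of a drug effect counts towards a category meant for events that are probably unrelated

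*Protocol*

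**What the plan says.** Protocol section 9.1.4 gives five causality categories and states that the Principal Investigator "must review each AE and make the determination of relationship of the event to the study treatment". *Definitely related* needs all of three criteria, *Probably related* three of four, and *Possibly related* two of four. *Unrelated* has no list but requires certainty.

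For *Probably* and *Possibly related*, criterion 1 is a reasonable temporal sequence. Criterion 2 begins "2) It could not readily have been produced by" and goes on to list other causes. Criteria 3 and 4 are "3) Disappears or is decreased upon discontinuation of the study treatment. (4) It follows a known response pattern to treatment with the study treatment".

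*Remotely related* is for events "judged likely to be unrelated to the study treatment". Its counting rule is "An AE may be considered unlikely if or when (must have two". Its first two criteria run "it does not follow a reasonable temporal sequence from administration of the study treatment. (2) It could not readily have been produced", and its last two "3) Disappears or is decreased upon discontinuation of the study treatment. (4) It does not follow a known response pattern to treatment".

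**The concern.** Criteria 1 and 4 of *Remotely related* were reversed from the relatedness lists; 2 and 3 were carried over unchanged. Absence of another cause and improvement on stopping point towards the drug, yet here they count towards calling the event probably unrelated. The two together are enough, whatever the timing or response pattern.

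At stake is the relationship label. It feeds the summary of treatment-emergent events by relationship (section 8.7.5.1) and one named safety measure, treatment-related events leading to discontinuation of study drug (section 8.2.3).

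**Working it through.** The plan gives no figure to reproduce, so the check is a side-by-side reading followed by an enumeration.

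**Side by side (section 9.1.4)**

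| Criterion | *Probably* / *Possibly* | *Remotely*, as written | Consistent with *Remotely*? |
|---|---|---|---|
| 1 Temporal sequence | present | absent | yes |
| 2 Ready alternative cause | none | none | no, not reversed |
| 3 Improves on stopping | yes | yes | no, not reversed |
| 4 Known response pattern | present | absent | yes |

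**Rules.** Let T = temporal sequence, U = no ready alternative cause, R = improves on stopping, P = known response pattern.

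- Definite: T and U and P. Its alternative-cause criterion is worded slightly differently and is treated here as U.
- Probable: at least 3 of {T, U, R, P}.
- Possible: at least 2 of {T, U, R, P}.
- Remote as written: at least 2 of {not T, U, R, not P}.
- Remote with 2 and 3 negated: at least 2 of {not T, not U, not R, not P}.

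R can be judged only if treatment was stopped. The 8 patterns of T, U and P are therefore run in three states. Where R cannot be assessed, criterion 3 scores 0 in every list. Section 9.1.8 gives one setting where that happens, for injection-related events: "For subjects who develop grade 1 or grade 2 events, continue therapy as per protocol".

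**Two worked cases, as written**

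- T, U, R and P all true: relatedness score 4, so Definite, Probable and Possible are all met. Remote score = 0 + 1 + 1 + 0 = 2, so Remote is met too. After negation the Remote score is 0.
- T only, R not assessable: relatedness score 1, so Possible is not met. Remote score = 0 + 0 + 0 + 1 = 1, so Remote is not met either. After negation it is 0 + 1 + 0 + 1 = 2, and Remote is met.

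**Full result (as written → after negating 2 and 3)**

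| | (a) Not stopped | (b) Stopped, improved | (c) Stopped, not improved |
|---|---|---|---|
| Patterns meeting Remote, of 8 | 4 → 4 | 7 → 4 | 4 → 7 |
| Definite also Remote | 0 of 1 → 0 of 1 | 1 of 1 → 0 of 1 | 0 of 1 → 0 of 1 |
| Probable also Remote | 0 of 1 → 0 of 1 | 3 of 4 → 0 of 4 | 0 of 1 → 0 of 1 |
| Possible also Remote | 2 of 4 → 0 of 4 | 6 of 7 → 3 of 7 | 2 of 4 → 3 of 4 |
| In no counted category | 2 → 0 | 0 → 0 | 2 → 0 |
| In exactly one of Possible-or-higher and Remote, of 8 | 4 → 8 | 2 → 5 | 4 → 5 |

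The error moves patterns in both directions.

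- (a) It adds T+U and U+P to Remote and removes T only and P only.
- (b) It adds T+U, U+P and T+U+P and removes none.
- (c) It adds none and removes T only, P only and T+P.

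The patterns in no counted category, in (a) and (c), are T only and P only. *Unrelated* is no fallback for them, because it requires certainty.

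**The case against.** The strongest reply is that the lists do not decide the category. Each category opens with a governing judgement, the lists are permissive, and the determination belongs to the Principal Investigator. An event with every feature of a drug reaction would be coded *Remotely related* only if the investigator also thought it probably unrelated. By the same reasoning, an event that meets no list can still be placed by that opening judgement. This stands: the text makes classification contradictory but does not force a wrong code. It does not supply a reading in which improvement on stopping, or the absence of another cause, supports unrelatedness.

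The consequences are also limited. No event is lost, discontinuations due to adverse events are summarised separately whatever their relationship (section 8.7.5.1), no inferential statistics are planned (section 8.7.5), and the efficacy endpoints are untouched. The pattern counts say nothing about how many events would be mislabelled. All of this is accepted.

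The correction is not a complete partition. With treatment stopped, 3 of 8 patterns still meet both *Possible* and *Remote*, and in state (c) that overlap rises from 2 patterns to 3. This is true, but it arises because both categories use a two-of-four threshold, which is separate from the missing negations.

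Finally, rechecking coded events may seem too much when nothing shows that investigators counted criteria. Nothing shows that they did not, and the study is small.

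**Conclusion.** The concern holds. Criteria 2 and 3 of *Remotely related* contradict the category's definition. The conflict is widest when treatment is stopped and the event improves: *Remote* then takes in the single Definite pattern, 3 of 4 Probable and 6 of 7 Possible. Negating the two criteria removes all overlap with Definite and Probable, and leaves no pattern without a counted category. Where treatment was not stopped, all 8 patterns then fall cleanly on one side.

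This rests on scoring the lists as counts and weighting nothing by frequency. No direction of bias is claimed. The effect on treatment-related events leading to discontinuation depends on which categories count as related, which the protocol does not state. If *Remote* counts as related, a shift between *Possible* and *Remote* changes nothing there; if it does not, the count changes. The correction should be made, but it concerns descriptive safety labels only.

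**What to change.** In category 4 of section 9.1.4, reverse criterion 2 so that it says the event could readily have arisen from the other causes listed there. Reverse criterion 3 so that it says the event does not disappear or lessen when study treatment is stopped. Criteria 1 and 4 and the two-of-four rule stay as they are.

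Have investigators confirm once, against the corrected list, the relationship of adverse events already coded. This should cover all categories, not only *Remotely related*, because the error takes some patterns out of that category as well as putting others in. A tie rule for the *Possible*/*Remote* overlap that remains when treatment was stopped is optional and not part of this error.

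The cost is two items of protocol wording and a single confirmation round in a study of up to 25 subjects, or the number enrolled by BLA submission.

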9.1.5 Treatment Given as a Result of the Event

The event impact in terms of treatment provided will be as either: none, medication administered, non-medication therapy administered, surgery, or other (with a specification).

9.1.6 Outcome Assessment

The outcome of the event will be assessed as either: resolved, resolved with sequelae, ongoing, or death. Only one AE per subject is allowed to have an outcome assessment as "death." If there are multiple causes of death for a given subject, only the primary cause of death will have an outcome of death.

9.1.7 Expected / Anticipated Adverse Events

The most common potential study drug-related adverse reaction reported is mild headache. Other adverse events likely to be related to the drug include mild to moderate diarrhea, nausea, and fatigue.

9.1.8 SC Injection-related Events

SC and IV injections of concentrated protein materials can be associated with injection-related AEs that impact the ability to safely and successfully deliver the drug. Local injection-site reactions may include pain/discomfort, induration, erythema, nodules/cysts, pruritus, ecchymosis, etc. For SC injections, bleeding, absorption of the drug, leakage of drug, and induration at the local injection site can be additional complications. Other AEs that are common to monoclonal antibody-based therapies are chills, headache, backache, malaise, fever, pruritus, rash, nausea, tingling, and hypertension.

SC injection-related events will be monitored according to the guidelines provided in [Section 16.2](#) (Division of AIDS Table for Grading the Severity of Adult and Pediatric Adverse Events [DAIDS AE Grading Table]). Injection-site reactions thought to be directly related to the injection are considered to be AEs of special interest, and a separate guideline for the acquisition of data related to this AE of special interest is provided in [Section 16.3](#).

For subjects who develop grade 1 or grade 2 events, continue therapy as per protocol. If a subject chooses to discontinue study treatment, the site should notify the protocol team leadership, and encourage the subject to complete any remaining study visits until the toxicity resolves.

For subjects who develop grade 3 events following study drug injection, the subject should be reevaluated closely until the AE returns to Grade ≤ 2 , at which time study treatment may be reintroduced at the discretion of the site investigator. If the *same* Grade 3 AE recurs following the next administration of study drug, study treatment must be permanently discontinued. Subjects experiencing Grade 3 AEs requiring permanent discontinuation of study treatment should be followed closely for resolution of the AE to Grade ≤ 2 and the team leadership must be notified.

Subjects with Grade 3 asymptomatic laboratory abnormalities in cholesterol, creatine kinase (CK) or triglycerides may continue study treatment.

For grade 4 events permanently discontinue therapy.

9.2 SERIOUS ADVERSE EVENTS (SAE)

A SAE is defined as any AE that:

- Results in death
- Is life threatening (the subject is at immediate risk of dying from the AE)
- Requires subject hospitalization or prolongs existing hospitalization
- Results in persistent or significant disability/incapacity
- Is a congenital anomaly/birth defect

Important medical events that may not result in death, be life-threatening, or require hospitalization may be considered a serious adverse event when, based upon appropriate medical judgement, they may jeopardize the subject and may require medical or surgical intervention to prevent one of the outcomes listed in this definition.

If a pregnancy occurs in a subject or partner of a male subject during a clinical study this must also be reported to CytoDyn, Inc. The Investigator should discuss the case with the Medical Monitor. Any pregnant subject must be followed up by the Investigator or designee until the child is born. Any AEs of the subject during pregnancy, that meets serious criteria, must be documented and reported to CytoDyn, Inc. Participants who become pregnant will be entered into the Antiretroviral Pregnancy Registry (<http://www.apregistry.com>).

9.3 REPORTING OF SERIOUS ADVERSE EVENTS

The Investigator is required to report all SAEs that occur during the time period specified in [Section 9.1.1](#). Once the Investigator becomes aware of an SAE, he/she must report the SAE to Amarex Safety Department within 24 hours:

CRO Medical Monitor	Attn: [name] Amarex LLC [name] [name] Email: [contact] [contact] [contact]
----------------------------	--

The Amarex Medical Monitor may request additional supporting documentation as it becomes available, such as lab reports, ECG reports, discharge summary, hospital notes, etc.

The Investigator is also responsible for reporting all SAEs to the appropriate Institutional Review Board (IRB) in accordance with local laws and regulations. The Investigator is responsible for maintaining documentation in the study file that indicates the IRB has been properly notified. Under 21 CFR 312.32(c), the sponsor is required to notify FDA and all participating investigators in an IND safety report (i.e., 7- or 15-day expedited report) of potentially serious risks from clinical trials or any other source as soon as possible, but no later than 15 calendar days after the sponsor receives the safety information and determines that the information qualifies for reporting. Participating investigators include all investigators to whom the sponsor is providing drug under any of its INDs or under any investigator's IND (21 CFR 312.32(c)(1)).

9.3.1 SAE Follow-Up

All subjects experiencing an SAE, including the discontinued subjects, must be closely followed until sufficient information is obtained to indicate a return to normal status or until the event stabilizes at a level acceptable to the investigator (i.e., recovery, return to baseline status, no further improvement expected, or death).

For each SAE indicated as an unresolved event on the initial report, regardless of whether the subject completed the study or withdrew, the site should submit a follow-up report with updated information.

10 DIRECT ACCESS TO SOURCE DATA/DOCUMENTATION

Subjects will be identified on eCRFs by a unique subject identification number and on source documents by name and date of birth. No personal identifier will be used in any publication or communication used to support this research study. The subject identification number will be used if it becomes necessary to identify data specific to a single subject.

The monitors, auditors, personnel authorized by the Sponsor, the local IRB, and the FDA are eligible to review medical and research records related to this study as a part of their responsibility to protect human subjects in clinical research and will be given direct access to source data and documentation (e.g., medical charts/records, printouts etc.) for source data verification, provided that subject confidentiality is maintained in accordance with local requirements. Access to electronic medical records may be governed by institution policy and each site will be required to ensure access while remaining compliant with institutional requirements.

11 QUALITY CONTROL AND QUALITY ASSURANCE

11.1 MONITORING REQUIREMENTS

In an effort to fulfill the obligations outlined in 21 Code of Federal Regulations (CFR) Part 312 and ICH guidelines which requires the Sponsor to maintain current personal knowledge of the progress of a study, the Sponsor's designated monitor will visit the center(s) during the study as well as maintain frequent telephone and written communication. The Investigator will permit the Sponsor to monitor the study as frequently as is deemed necessary and provide access to medical records to ensure that data are being recorded adequately, that data are verifiable and that protocol adherence is satisfactory.

The Investigator will permit representatives of the Sponsor and/or designated CRO to inspect all eCRFs and corresponding study subject original medical records (source documents) at regular intervals throughout the study. Subject original medical records and other relevant data must be available to support all data recorded in the eCRF. In addition to the original medical records, these data may include but are not limited to, study, laboratory and diagnostic reports, neurological examination results, etc.

Site inspections serve to verify strict adherence to the protocol and the accuracy of the data being entered on the case report forms, in accordance with federal regulations. A Monitoring Log will be maintained at each study site which the monitor will sign, date and state the type of visit.

The Investigator should be aware that the study site and subject records may be inspected by the Sponsor and or representatives of the designated CRO, FDA or other regional regulatory authority.

For the IA, a cut-off date for data collection and monitoring will be determined and sites will be requested to provide current information up to the cut-off date.

